3.0 STUDY SCHEMA

4.0 INTRODUCTION

4.1 Background and Significance to the Field

For opioid use disorder patients in the U.S. and most of the rest of the world, detoxification or detoxification followed by short-term residential treatment, with the goal of achieving long-term abstinence from opioid misuse is a mainstay of treatment. Although it is widely believed that many patients treated in this way will rapidly relapse to opioid misuse – leading to a costly and ineffectual cycle of readmission for repeated detoxifications – there is scant data on opioid use outcomes following discharge from these programs. Searches of PubMed, NIH Reporter, and ClinicalTrials.gov for “clinical outcomes following opioid detoxification” and the like, mostly

reveal studies focused on detoxification methods, medication schedules, withdrawal symptomatology, tolerability and the proportion of patients completing detoxification.¹⁻⁶ Three studies,⁷⁻⁹ two of them from Europe, focused on subsequent outcomes (e.g., use, misuse, relapse) after patients completed detoxification. Gossop et al⁷ followed eighty patients discharged from 21-day methadone withdrawal programs at two United Kingdom hospitals between 1984 and 1986. Seventy-one percent used opioids within the first six weeks of discharge, and 81% used opioids at some point during the six-month follow-up, though at the six-month endpoint 51% were opioid-free. Broers et al⁸ followed 73 patients discharged from a Geneva, Switzerland 15-day (average) methadone tapering program between 1994 and 1995. Sixty-five percent were using drugs again (half of them regularly) within the first four weeks. At the six-month endpoint half of the population was physically dependent again. Chutuape et al⁹ followed 113 patients discharged from a 3-day medical (mostly clonidine) detoxification program in Baltimore, Maryland between May and November 1996. At the one-, three- and six-month post-discharge assessments, 25-36% reported almost daily use, 21-30% reported no use, and the remainder reported occasional use. Overall, the mean number of days of heroin use decreased from 28 days (in the month prior to admission) to 11-14 days. In addition, several studies, most of them randomized trials of buprenorphine detoxification, collected limited datasets on post-detoxification outcomes which were disappointing (only 3-47% self-reporting abstinence, and only 7-31% producing negative urine drug screens over one- to three-month follow up periods).¹⁰⁻²⁰

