5.0 OBJECTIVES

5.1 Primary Objective

The primary objective is to follow a group of participants with opioid use disorder to estimate treatment-as-usual rates of opioid use clinical outcomes following discharge to the community from detoxification and/or short-term residential programs.

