13.3 Statistical Methods for Primary and Secondary Outcomes

The primary objective of this study is to estimate opioid use rates, via various measures of use (Section 13.1.1), overall and separately for the sub-groups defined by use of medication-assisted treatment and type of treatment received at the enrolling site. Secondary exploratory analyses will involve modeling of opioid use as a function of certain independent predictors (see Section 13.2). For the primary objective all continuous variables (e.g., percent use days in the first week) will be summarized using the following descriptive statistics: n (non-missing sample size), mean, standard deviation, median, maximum and minimum. The frequency and percentages (based on the group-specific sample size) of observed levels will be reported for all categorical measures.

To evaluate secondary exploratory outcomes, two main sub-groups from the observational cohort are (1) participants who receive any medication-assisted treatment and (2) participants who do not receive medication-assisted treatment. All outcomes listed in Section 13.1.1 will be calculated separately for each of these subgroups of the observational cohort, as well as in the overall study sample. Program type, that is, short-term detoxification vs. short-term residential rehabilitation, will also define groups to be separately analyzed.

For modeling the days to first opioid use and days to regular opioid use outcomes measures, a Cox regression model will be used after an assessment of the proportional hazards assumption. Should the key proportional hazards assumption be violated for a particular outcome and covariate, alternative models will be considered. The second set of outcomes relate to the number of days of opioid use. It is anticipated that the number of days of use will be non-normal, however we elect to analyze the data via a *t*-test which is fairly robust to misspecification of the underlying outcome distribution. Quantile regression may be used if modeling with multiple covariates is appropriate. For UDS-based outcomes, the dependent variable is binary (i.e., indicator of use or indicator of missingness) so univariate comparisons will be made using Pearson's χ^2 and any multivariate modeling will be implemented using logistic regression.

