### **2.3 Treatment Plans**

To evaluate the outcomes, two main sub-groups from the observational cohort are (1) participants who receive any medication-assisted treatment (MAT) and (2) participants who do not receive medication-assisted treatment. Assessment of the participant's intention for treatment after discharge to community (i.e., leaving the detox and/or short-term residential unit) was assessed at the Day 0 visit (Community Discharge Plan). On the Medical Management (MM) Community Treatment form, at weeks 1, 4 and 8, participants were asked what treatment(s) he/she was engaged in, with the options being

- (1) MAT with buprenorphine maintenance
- (2) MAT with injectable naltrexone
- (3) MAT with oral naltrexone
- (4) MAT with methadone maintenance
- (5) MAT with inpatient detox
- (6) Psychosocial
- (7) Referral to other community-based treatment
- (8) Declined further treatment.

A participant will be categorized as having received any medication-assisted treatment post-discharge if at any visit (Weeks 1, 4, and 8), the treatment plan engaged in includes medication-assisted treatment.

Program type and high severity vs. low severity at baseline will also define groups to be separately analyzed. The program type subgroups will be defined based on the length of stay in the detox and/or residential facility. The date of admission to the detox unit is found on the Detoxification Utilization Summary form and the corresponding dates of discharge for both the detox unit and residential facility are found on the enrollment form. If the subject was discharged to the community from the residential facility, the total time in detox and the residential facility will be calculated. The difference between admission and discharge dates will be tabulated and categorized based on the following groupings: (1)  $\leq 7$  days, (2) 8-20 days and (3)  $\geq 21$  days.

High severity and low severity opioid use level at baseline will be defined as computed for the main CTN-0051 study stratification factor (i.e.  $< 6$  bags vs.  $\geq 6$  bags). To compute the opioid severity level, if the primary opioid of use in the last 7 days was not heroin or the route of administration is not IV-injection then that participant is defined as a low severity user. For IV heroin users where the quantity is not provided in bags but in dollars, bags are estimated as the dollar amount/10 rounded to the nearest integer.

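### The SAP redefines program type as length of stay, so the detoxification versus residential estimates described in the protocol have no planned output

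*SAP*

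**What the plan says.** Protocol 13.3 opens by stating the primary objective as estimating opioid use rates "overall and separately for the sub-groups defined by use of medication-assisted treatment and type of treatment received at the enrolling site". Its next paragraph, which begins with secondary exploratory outcomes, first takes up the medication-assisted treatment groups and then adds: "Program type, that is, short-term detoxification vs. short-term residential rehabilitation, will also define groups to be separately analyzed". The objective in Protocol 5.1 is broader and names no subgroup. It is to "estimate treatment-as-usual rates of opioid use clinical outcomes following discharge to the community from detoxification and/or short-term residential programs".

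SAP 2.3 keeps the term but gives it another meaning: "The program type subgroups will be defined based on the length of stay in the detox and/or residential facility". On the calculation it says: "If the subject was discharged to the community from the residential facility, the total time in detox and the residential facility will be calculated". It then says: "The difference between admission and discharge dates will be tabulated and categorized based on the following groupings", and lists ≤7, 8-20 and ≥21 days. On data sources it says that "the corresponding dates of discharge for both the detox unit and residential facility are found on the enrollment form".

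SAP 5.0 restates the primary objective but refers only to the subgroups as the SAP defines them. The end of SAP 2.3 applies those subgroups to every outcome. SAP 3.2.1 repeats the protocol's list of possible predictors, which includes the treatment type before discharge.

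**The concern.** The same label stands for two different variables. In the protocol, program type has two levels and describes the kind of program. In the SAP it has three levels and describes how many days the participant stayed, whichever facility those days were spent in. The SAP does not link any band to a program, does not mark the change as a departure from the protocol, and gives no reason for it.

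At stake is a set of descriptive results that the protocol leads its readers to expect: opioid use after discharge from detoxification, and separately after discharge from short-term residential treatment. If the SAP is followed as written, those results are not tabulated. Length of stay may well be informative, but it answers a different question, because it also depends on how long each participant chose to remain.

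**Working it through.** The plan gives no figure to reproduce here. The check is a comparison of definitions and a count of the planned outputs.

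1. **Definition in the protocol (13.3).** Two groups: detoxification and residential rehabilitation. Membership depends on the program.

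2. **Definition in the SAP (2.3).** Three groups: ≤7, 8-20 and ≥21 days. Membership depends on total days from admission to discharge. Detoxification and residential days are added together for anyone discharged from the residential facility.

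3. **Does the second definition determine the first?** Take one participant discharged from a detoxification unit on day 12 and another discharged from a residential facility after 12 total days. Both fall in the 8-20 band, so the rule assigns them to the same group although their programs differ. The bands would reproduce program type only if stays in the two programs did not overlap and each band were assigned to a program. The documents establish neither condition, and they give no distribution of stay by unit.

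4. **Count of planned outputs in the SAP.** The outcome tables are Tables 8 to 19, which is 12 tables: 4 outcomes × 3 groupings (medication-assisted treatment, length of stay, baseline severity). The Kaplan-Meier figures are Figures 2 to 7, which is 6 figures: 2 time-to-event outcomes × the same 3 groupings.
   - By length of stay: Tables 9, 12, 15 and 18 and Figures 3 and 6, so 4 of 12 tables and 2 of 6 figures.
   - By detoxification versus residential: 0 of 12 tables and 0 of 6 figures.
   - Table 5, which counts participants in each subgroup, also uses length of stay and has no detoxification versus residential rows.

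5. **Is the protocol's variable obtainable?** The rule for summing stays applies only to participants discharged from the residential facility, so the analyst must already know who they are. The SAP places separate discharge dates for the two units on the enrollment form. The two-group split can therefore be derived from items that the SAP already uses. The form itself is not among the documents, so this rests on the SAP's description of it.

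6. **What remains of the protocol's grouping.** Treatment type before discharge stays on the list of possible predictors in SAP 3.2.1, and SAP 5.5 provides for exploratory modeling. The SAP gives that predictor no separate definition and no table or figure shell.

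**The case against.** Several points on the other side have force.

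- **The place in the objectives.** A reader might infer that a subgroup named in the primary objective has been lost. The documents do not clearly support that. Section 5.1 names no subgroup. In 13.3, treatment type appears in the sentence on the primary objective, but the definition of program type comes in the paragraph on exploratory outcomes. Treating the two phrases as the same grouping is the natural reading, but it is a reading.
- **Never estimated.** This goes too far, because an exploratory model could still include treatment type. What can be said is that no subgroup output is planned.
- **The bands must mix programs.** A reader might infer this from the background in Protocol 4.1, where the cited detoxification programs include a "15-day (average) methadone tapering program" as well as 3-day and 21-day programs. Those programs ran in other settings between 1984 and 1996 and say nothing about stays at the five sites here.
- **A diluted contrast.** A numerical attenuation would need a stay distribution by unit and a mapping of bands to programs. Neither is given, so no size can be attached.
- **A wrong test.** A reader might infer that the two-sample t-test in SAP 5.5 has been set against three groups. The SAP does not assign it to the bands, and the length-of-stay shells are purely descriptive.
- **Misleading output.** The affected tables and figures are titled by length of stay, so their reader would probably not take them for program type. The relabeling occurs in SAP 2.3.
- **Discharge unit is not a pure measure either.** Someone who leaves detoxification before a planned transfer would count as detoxification, and a long detoxification stay followed by one residential day would count as residential. This stands, and it belongs in the interpretation of the proposed variable.

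None of these points supplies the missing output or explains why the definition changed.

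**Conclusion.** The point holds as an unexplained change between protocol and SAP, with a definite but limited effect. A grouping that the protocol defines and says will be analyzed separately has no table or figure in the SAP, and its name has been given to a different variable. The overall estimates and the medication-assisted treatment and severity subgroups are not affected. The study is descriptive, so no hypothesis test or error rate depends on this.

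The conclusion rests on the text alone: total days do not by definition identify the program. It does not rest on any assumption about how much the bands and programs overlap at these sites, which the documents leave open. The change is worth making because it restores a described estimate from data that appear to be in hand.

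**What to change.** In SAP 2.3, define program type as the unit from which the participant left for the community, detoxification unit or residential facility, derived from the unit-specific discharge dates on the enrollment form. Add these two groups to Table 5 and, for each outcome, to the tables and Kaplan-Meier figures, either as extra columns and curves in Tables 9, 12, 15 and 18 and Figures 3 and 6 or as separate shells. Keep the length-of-stay bands as a grouping under their own name and stop calling them program type. Add a sentence noting that discharge unit can partly reflect early leaving, so differences between the two groups should not be read as effects of the program.

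If the replacement was deliberate, the SAP should at least say so and justify it as a departure from Protocol 13.3. That would settle the inconsistency but would still leave the estimates unreported.

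The cost is a short change of wording, one derived variable and a little more output. On the SAP's description of the enrollment form, no new data are needed.

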### 3.0 GENERAL CONSIDERATIONS

#### 3.1 Terminations

All participants will be followed for the duration of the study (CTN-0051-A2) unless they withdraw consent, die, or the investigator (site PI or LI) or sponsor decides to discontinue their enrollment for any reason. Reasons for the investigator or sponsor terminating a participant from the study may include, but are not limited to, the participant becoming a threat to self or others, lack of funding, or early termination of the study by the Data and Safety Monitoring Board (DSMB) for safety or other reasons.

#### 3.2 Sample Size and Power Calculations

##### 3.2.1 Rationale for Sample Size and Statistical Power

No formal statistical hypothesis tests will be calculated for this study; therefore, there is neither sample size nor statistical power calculations. The study population is a convenience sample and it is anticipated that each participating site should be able to enroll approximately 60 participants for a total of approximately 360 participants. While the main objectives of this study are descriptive in nature, such as estimating the opioid use rate eight weeks after discharge to the community, it may be of interest to evaluate whether these opioid use outcomes are associated with certain covariates. Potential independent predictors of opioid use include: age, gender, race, ethnicity, use of medication-assisted treatment, and type of treatment received prior to discharge to the community.

##### 3.2.2 Number of Sites

Five sites with inpatient detoxification programs and/or short-term residential treatment programs associated with CTN-0051 will recruit participants.

##### 3.2.3 Projected Number of Participants per Site

Approximately 60 participants will be recruited at each of the approximately six sites.

##### 3.2.4 Detectable Effect Sizes

Table 1 summarizes detectable effect sizes for the two outcomes: (a) time to first opioid use, and (b) time to first regular opioid use. The detectable hazard ratios (HRs) are calculated for various values of the standard deviation of the outcome measure and the overall percent of participants who had (a) used opioids or (b) regularly used opioids during the eight week follow-up period. Total sample sizes of 280, 320 and 360 were considered. If the target sample size of 360 is reached, and 60-70% of participants use or regularly use opioids by the week 8 follow-up visit, then there will be at least 80% power to detect a HR of approximately 1.46 with a type I error rate of 5%. On the other hand if only 320 participants are enrolled, then the detectable HR is around 1.50 and for 280 participants, then the detectable HR is around 1.40-1.75.

**Table 1.** Detectable hazard ratios for the outcomes measures time to (a) first opioid use, and (b) first regular opioid use

Total Sample Size	Detectable Hazard Ratio	Power (%)	Proportion of Participants who Used Opioids/ Regularly Used (%)	Standard Deviation of the Number of Days to First Opioid Use/Regular Use
280	1.75	83%	60%	0.4
	1.40	82%	70%	0.5
320	1.50	81%	60%	0.5
	1.47	83%	70%	0.5
360	1.47	82%	60%	0.5
	1.45	84%	70%	0.5

Table 2 summarizes detectable effect sizes for the outcomes based on the number of days of opioid use during the eight weeks post-discharge to the community of the study. The detectable mean differences for the two-sample *t*-test are calculated for various values of the group-specific mean and standard deviations of the outcome measure. Total sample sizes of 280, 320 and 360 were considered. If participants in one group use opioids on average two weeks out of the month, then we can detect a difference of 1.5 use days with at least 80% power (assuming a type I error rate of 5%) if the target sample size of 360 is achieved. Similarly, if participants in one group use approximately three weeks out of a month, then we can detect a difference of 1.5 days. With 320 participants enrolled, a mean difference of 1.5 days can still be detected with at least 80% power, but the detectable difference increases to 2.8 days with a total sample size of 280.

Table 2. Detectable differences in means for the number of days of opioid use during the eight weeks of follow-up				
Total Sample Size*	Detectable Difference** in Means (days)	Power (%)	Mean (SD) in Group 1	Mean (SD) in Group 2
280	2.8 days	84%	14.0 (5.0)	15.8 (6.0)
	1.5 days	88%	21.0 (4.0)	22.5 (4.0)
320	1.5 days	83%	14.0 (3.5)	15.5 (5.5)
	1.5 days	83%	21.0 (3.5)	22.5 (5.5)
360	1.5 days	82%	14.0 (3.5)	15.5 (6.0)
	1.5 days	88%	21.0 (4.5)	22.5 (4.5)

\* Assumes equal distribution of participants across the two groups.  
 \*\* The difference is defined as the mean in Group 2 – mean in Group 1.

Table 3 summarizes detectable effect sizes for the outcomes based on urine drug screen testing. The detectable odds ratios are calculated for various values of the proportion of participants in each subgroup and the event rate in Group 1. Total sample sizes of 280, 320 and 360 were considered. For various values of the percent of participants in each subgroup, an odds ratio of around 2 (1.85-2.40) can be detected assuming an event rate of 50% in Group 1 with at least 80% power and total sample sizes of 280 to 360.

Table 3. Detectable odds ratios for UDS-based outcomes				
Total Sample Size	Detectable Odds Ratios	Power (%)	Proportion in Group 1 (%)	Event Rate in Group 1 (%)
280	2.40	81%	20%	50%
	2.15	81%	30%	50%
	2.05	82%	40%	50%
	1.98	80%	50%	50%
	2.00	80%	60%	50%
	2.10	80%	70%	50%
	2.40	82%	80%	50%
320	2.30	82%	20%	50%
	2.05	82%	30%	50%
	1.98	83%	40%	50%
	1.90	81%	50%	50%
	1.98	84%	60%	50%
	2.00	80%	70%	50%
	2.30	84%	80%	50%
360	2.15	81%	20%	50%
	1.95	81%	30%	50%
	1.85	80%	40%	50%

Table 3. Detectable odds ratios for UDS-based outcomes				
Total Sample Size	Detectable Odds Ratios	Power (%)	Proportion in Group 1 (%)	Event Rate in Group 1 (%)
	1.85	82%	50%	50%
	1.85	81%	60%	50%
	1.95	82%	70%	50%
	2.15	82%	80%	50%

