2.3 Sample Size and Study Population

Participants will be a convenience sample of approximately three hundred sixty (360) opioid dependent patients leaving detoxification or short-term residential units at sites participating in CTN-0051. Approximately 60 participants will be recruited at each of approximately six sites.

Since this study utilizes a convenience sample and the objectives are to simply describe opioid use post-discharge, only detectable effect sizes were calculated (i.e., no sample size calculations performed). These effect sizes considered the evaluation of the association between post-baseline opioid use and a binary covariate such as gender, and use of medication-assisted treatment. Results of the effect size calculations are shown in Section 13.2.

[figure not shown]

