### 3.3 Software

All analyses will be performed utilizing SAS® version 9.3 or higher. All statistical tests will be conducted at the 5% Type I error rate (two-sided). When multiple tests are conducted, the chance of finding a significant difference in one of the tests, when in fact no difference exists, is greater than the stated Type I error rate. The investigators are aware of the multiple testing issues and will interpret results with caution and use confidence intervals where possible.

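### Table 1's SD column works only as a covariate SD, so the 80% power stated for HR about 1.46 at N=360 needs a roughly even split that is not mentioned, and the N=280 range is unreliable

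*SAP*

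**What the plan says.** SAP 3.2.4 and Protocol 13.2.3 carry the same text and tables. The headline sets two conditions, "If the target sample size of 360 is reached, and 60-70% of participants use or regularly use opioids by the week 8 follow-up visit", and concludes "then there will be at least 80% power to detect a HR of approximately 1.46 with a type I error rate of 5" per cent. It then gives a detectable HR of around 1.50 for 320 participants and around 1.40-1.75 for 280.

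On the method, the text says "The detectable hazard ratios (HRs) are calculated for various values of the standard deviation of the outcome measure" and the overall percentage with an event. Table 1 prints that SD as 0.5 in five of its six rows, for example "360 1.47 82% 60% 0.5" (N, HR, power, events, SD). The sixth, N=280 with HR 1.75, has 0.4.

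Protocol 2.3 says the effect sizes concern the "evaluation of the association between post-baseline opioid use and a binary covariate such as gender, and use of medication-assisted treatment". An equal split is stated only in the footnote to Table 2. Table 3 varies the share in Group 1 from 20% to 80% and concludes that "For various values of the percent of participants in each subgroup, an odds ratio of around 2 (1.85-2.40) can be detected".

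**The concern.** An SD of 0.4 or 0.5 days is implausible for a time to use measured over eight weeks, and the usual Cox power formula has no place for an SD of the outcome. It does need the SD of the covariate, which for a binary covariate with a share q in one group is sqrt(q(1-q)). That equals 0.5 at 50/50 and 0.4 at 20/80, the two values printed.

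On that reading the headline rests on the most favourable split without saying so, and the wrong label stops a reader from recovering the condition from the table. The covariates of interest, such as gender and use of medication-assisted treatment, are not balanced by design in a convenience sample. A reader could take an unremarkable HR near 1.5 in an uneven subgroup as having been examined with 80% power. The three sample sizes are also not compared on the same footing.

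**Working it through.** **Inputs.** N, HR, event proportion, SD and printed power come from Table 1. The two-sided 5% level comes from SAP 3.3. Events are taken as N times the event proportion, because Table 1 states no allowance for dropout.

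**Formula.** Power = Phi( sqrt(N × event proportion) × SD × ln(HR) − 1.96 ), with SD = sqrt(q(1−q)).

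**Step 1: reproduce Table 1, reading the SD column as the covariate SD.**

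| N | HR | Events | SD (split) | Printed power | Recomputed |
|---|---|---|---|---|---|
| 280 | 1.75 | 168 | 0.4 (20/80) | 83% | 82.7% |
| 280 | 1.40 | 196 | 0.5 (50/50) | 82% | **65.4%** |
| 320 | 1.50 | 192 | 0.5 | 81% | 80.2% |
| 320 | 1.47 | 224 | 0.5 | 83% | 82.2% |
| 360 | 1.47 | 216 | 0.5 | 82% | 80.8% |
| 360 | 1.45 | 252 | 0.5 | 84% | 83.9% |

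For N=360 and HR 1.47: sqrt(216) × 0.5 × ln(1.47) = 2.831; 2.831 − 1.96 = 0.871; Phi = 80.8%. Five rows agree within about 1.2 points. A one-sided test does not fit (88.2% and 90.4% for the two N=360 rows).

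**Step 2: the row that fails.** For N=280, HR 1.40, 70% events: sqrt(196) × 0.5 × ln(1.40) = 2.355; 2.355 − 1.96 = 0.395; Phi = 65.4%. A one-sided test gives 76.1%, still short of 82%. The HR that gives 82% power is exp((1.96 + 0.915)/7) = 1.51.

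**Step 3: the headline at other splits.** N=360, HR 1.46. The splits come from Table 3's grid.

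| Split | Power, 60% events (216) | Power, 70% events (252) | HR for 80% power, 60% / 70% events |
|---|---|---|---|
| 50/50 | 79.4% | 85.2% | 1.46 / 1.42 |
| 40/60 | 77.8% | 83.7% | 1.48 / 1.43 |
| 30/70 | 72.2% | 78.6% | 1.52 / 1.47 |
| 20/80 | 60.4% | 67.1% | 1.61 / 1.55 |

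The last column is exp(2.80 / sqrt(N × event proportion × q(1−q))). For 20/80 and 60% events: exp(2.80 / sqrt(216 × 0.16)) = 1.61.

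**Step 4: the upper end at N=280.** At 60% events and the printed 83% power (1.96 + 0.954 = 2.914), a 50/50 split needs exp(2.914 / (0.5 × sqrt(168))) = 1.57. The same calculation for N=320 gives exp(2.914 / (0.5 × sqrt(192))) = 1.52. At a common even split, going from 320 to 280 participants therefore moves the HR from 1.52 to 1.57. The rest of the way to 1.75 comes from the 20/80 split.

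**Step 5: how far the approximation can be trusted.** The formula ignores which group has the higher hazard. A log-rank simulation (exponential times, 56 days, 4,000 runs per setting, N=360, HR 1.46, 60-70% events) gave 65-70% power when the higher-hazard group is 20% of the cohort and 54-63% when it is 80%. For 30% and 70% it gave 76-81% and 69-76%.

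**The case against.** The strongest reply is that little depends on this table. Both documents say that no formal hypothesis tests are planned, the sample is one of convenience, no sample size was calculated, and the modelling is secondary and exploratory. SAP 3.3 promises cautious interpretation and confidence intervals where possible, and these would show the actual precision. That stands, and it limits the weight. It does not make the stated power right without its condition. SAP 3.3 also sets a two-sided 5% level, and SAP 5.5.2 plans to determine whether outcomes differ significantly by minority or gender status.

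A second reply is that the condition is mislabelled rather than absent, since 0.5 is printed beside both N=360 rows. That is true, and relabelling is the core of the fix. Under the present label, however, no reader would take 0.5 as a 50/50 split.

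Four stronger readings are tempting, and the documents do not support them:

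- That the claim fails at anything other than exactly 50/50. At 70% events, HR 1.46 keeps 80% power down to about 32/68, and moving from 50/50 to 40/60 costs under 2 points at either event rate.
- That the N=320 and N=360 rows are arithmetic errors. They reproduce once the column is read correctly.
- That the text presents a simple worsening from HR 1.50 to 1.75 as enrolment falls. It gives 1.40-1.75 for N=280, and that range starts below the figure for N=320.
- That the gender or treatment comparisons are shown to have 60-79% power. No prevalence is given for either, and Table 3 is an illustrative grid for another outcome that also includes 40-60% shares.

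**Conclusion.** The point holds as a labelling and completeness defect, together with one plain arithmetic error. Over the whole 60-70% event range, the 80% power stated for HR about 1.46 at N=360 requires a roughly even split. At 60% events it is met only to rounding even at 50/50 (79.4%). For covariates split 20/80 to 30/70, power is about 60-79% by the formula, and somewhat wider once the direction of the effect is allowed for.

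The N=280 range is unreliable at both ends. The upper end, 1.75, is correct for a 20/80 split but cannot be compared with the other sample sizes. The lower end, 1.40, has about 65% power rather than 82%.

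These results assume the Cox formula with covariate SD, events equal to N times the event proportion, a two-sided 5% level, and Table 3's splits. The error at HR 1.40 needs no assumption about prevalence, only the same reading of the SD column that reproduces the other five rows. This should be corrected, but no estimate or planned analysis depends on it.

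**What to change.** In SAP 3.2.4 and Protocol 13.2.3:

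- Relabel the last column of Table 1 as the covariate split (or covariate SD), and amend the sentence that calls it the SD of the outcome.
- Correct the N=280, HR 1.40 row. At 70% events and an even split, 82% power needs an HR of about 1.51.
- Show N=280, 320 and 360 at the same splits, for example 20%, 30%, 40% and 50%, as Table 3 does, and restate the N=280 and N=320 sentence at one split.
- Restate the headline along these lines: with 360 participants and 60-70% events, the HR detectable with 80% power is about 1.42-1.46 for an evenly split covariate, rising to about 1.55-1.61 for a 20/80 split.

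The cost is one recalculated table and a few reworded sentences. The stated figure becomes less favourable for uneven subgroups. Enrolment and data collection do not change.
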